1.0 Study Summary

Study Title	Scarcity narratives and AUD
Study Design	Adults with Alcohol Use Disorder (AUD) will be enrolled in the study and complete two online sessions where the effects of exposure to scarcity narratives on delay discounting and alcohol demand will be investigated. Participants will be randomly assigned to one of two scarcity narrative groups (active or control), balanced by discounting rate and sex. Delay discounting and alcohol demand will be evaluated pre and post exposure to the narratives.
Primary Objective	The primary objective is to test the theory of Reinforcer Pathology via manipulation of the temporal window with exposure to a scarcity narrative. The primary outcome measures of this study are the extent to which scarcity narratives decrease an individual's temporal window and increase their alcohol valuation, compared to baseline.
Secondary Objective(s)	Investigate the effects of scarcity narratives on delay discounting and demand in individuals with AUD
Study Population	Individuals with Alcohol Use Disorder (AUD)
Sample Size	112
Research Intervention(s)/ Investigational Agent(s)	Participants will complete two online surveys that will last approximately 1h each. The survey will collect data on AUD severity, demographics, patterns of alcohol consumption, DD, and alcohol demand pre and post exposure to scarcity narrative.
Study Duration for Individual Participants	The study will have a duration of two online sessions of approximately 1h each.
Acronyms and Definitions	AUD = Alcohol Use Disorder SUD = Substance Use Disorder DD = Delay Discounting RP = Reinforcer Pathology AI = Artificial Intelligence

2.0 Objectives

2.1 *Describe the purpose, specific aims, or objectives of this study:*

The goal of the present study is to test reinforcer pathology via manipulation of the temporal window (i.e., shorten the temporal window with exposure to a scarcity narrative). Another goal of the present study is to evaluate whether a voice recording can enhance the effects of a previously published scarcity narrative, compared to exposure to the written narrative only.

2.2 State the hypotheses to be tested:

We hypothesize a Group (Scarcity vs. Control) x Time (baseline vs. post) interaction. Specifically, we expect that participants exposed to an active scarcity narrative will present a shorten temporal view, as measured by Delay Discounting (DD), and increase demand for alcohol compared to baseline, whereas the control group would not show any changes between baseline and post intervention measures.

3.0 Background

3.1 Summarize the relevant prior research on this topic and gaps in current knowledge within the field of study:

RP suggests that substance use disorders results from a short temporal window of reinforcer integration, as indexed by a high DD rate. Data shows that DD serves as a behavioral marker for addiction and a predictor for therapeutic outcomes. Furthermore, a short temporal window increases the valuation of brief, immediate, and intense reinforcers (e.g., drugs), and decreases the value of reinforcers that are less intense and variable over time. RP has been mechanistically tested with manipulations that both increase the temporal window (i.e., decreases DD), such as episodic future thinking, or decrease the temporal window (i.e., increases DD), such as exposure to scarcity narratives. Although exposure to scarcity narratives has been shown to increase DD, few studies have investigated its effects on alcohol valuation, as measured through demand. Thus, the goal of the present study is to investigate the effects of scarcity narratives on both DD and demand in participants with AUD.

3.2 Describe any relevant preliminary data:

Previous online and in-laboratory studies from our group and others have shown that exposure to scarcity narratives increase DD in individuals with AUD, cocaine use disorder, smokers, overweight, and obese population. However, empirical evidence on the effects of scarcity on demand and drug valuation are scarcer.

3.3 Based on the existing literature, provide the scientific or scholarly rationale for and significance of your research and how will it add to existing knowledge:

To date, only two studies investigated the effect of scarcity narrative on DD in AUD population. Furthermore, only one of them included demand measures to assess alcohol

valuation. Thus, it is unclear how exposure to a scarcity narrative impacts both DD and alcohol valuation in AUD participants. In this study, we hypothesize that exposure to active scarcity narratives will increase DD and alcohol valuation as measured through demand compared to exposure to a control narrative. Specifically, we expect that participants exposed to an active scarcity narrative will present a shorten temporal view, as measured by Delay Discounting (DD), and increase demand for alcohol compared to baseline, whereas the control group would not show any changes between baseline and post intervention measures.

4.0 Study Endpoints

4.1 *Describe the primary and secondary **study** endpoints. See links below for discussion of study endpoints and how they may differ from study objectives. These are most common in clinical trials but are sometimes applicable to other types of biomedical research, as well as social, behavioral, or educational research. See link below for a discussion.*

https://docs.google.com/document/d/1Wocz7K7a0hCQJPPO_khh511SQQjhGDDGHzcOPRHR5Tw/edit?usp=sharing

Primary:

Change in Delay Discounting: Change in discounting rates will be compared within-subjects across sessions and between groups.

Change in Alcohol Demand: Change in alcohol demand will be compared within-subjects across sessions and between groups.

Alcohol craving: Change in alcohol craving will be compared within-subjects across sessions and between groups.

Subjective time perception: Change subjective time perception will be compared within-subjects across sessions and between groups.

4.2 *Describe any primary or secondary **safety** endpoints. These should be included for all studies that are greater than minimal risk. (Minimal risk: The probability and magnitude of harm or discomfort anticipated in the research that are not greater in and of themselves than those ordinarily encountered in daily life or during the performance of routine physical or psychological examinations or tests.):*

These procedures are not more than minimal risk.

5.0 Study Design and Statistical Analysis Plan

5.1 *Describe the basic study design/approach (e.g., qualitative study using five focus groups of first year students to describe assimilation into the university community; randomized controlled trial of a behavioral change intervention to increase dietary intake of whole grains; pre- post-test evaluation of new pedagogical techniques to improve adult literacy):*

The study will use a within-between design. Adults with AUD will be randomly assigned to two groups (active or control), balanced by discounting rate and sex. All participants will provide measures for all assessments pre and post exposure to the scarcity (or control) narrative.

5.2 *Describe corresponding data analysis plan/approach (e.g., content analysis of focus group transcripts; descriptive analysis followed by linear regression modeling; nonparametric analysis of pre- and post-test measures):*

Demographic characteristics will be summarized using descriptive statistics. We will compare outcome measures using a repeated measures ANOVA with active vs. control narratives as explanatory variables. Outcomes of interest include delay discounting and alcohol demand.

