8.0 Procedures Involved

8.1 *Describe and explain the study design:*

Adults with alcohol use disorder will be randomly assigned to one of two scarcity narrative groups narrative (active vs. control), balanced discounting rate and sex. We will enroll approximately 160 participants in order to conclude with 112 completers (56 per group).

The procedure will include two sessions. During the first session, participants will complete all the assessments via an online survey without any independent variable. After the first session, participants will be randomized to one of two groups. During the second session, participants will be initially exposed to one of the scarcity narratives (active vs. control). They will be asked to read the narrative while also listening to the narrative on audio. They will listen to either a male or female voice. The voice will be matched based on sex. They will be asked to vividly imagine that this narrative applies to them. Next, participants will complete the assessments in the presence of these narratives.

All dependent variables will be measured pre and post exposure to the scarcity narrative for all participants. Thus, narrative effects will be measured within-subject. Comparisons between active and control narratives will conducted between groups.

8.2 *Provide a description of:*

- *All research procedures being performed*
- *If the study has more than one procedure, session, and/or subject population, describe each procedure, session, and/or study population separately. For complex studies, you are encouraged to include a figure or chart.*

Participants in our REDCap database will be contacted if they have given prior permission to be contacted for future studies. Participants will be screened again for eligibility for the current study using a Qualtrics online survey.

Eligible participants will complete two online surveys on Qualtrics. The first survey will serve as the baseline. In the second survey, they will be exposed to one of the scarcity narratives and then they will answer the survey.

8.3 *Describe:*

- *Procedures or safeguards intended to reduce the probability and magnitude of risks. (For example: Reducing the risk of injury in a virtual reality study either by having the subjects sit during the study or by providing an obstacle-free space for walking.)*
- *Be sure to describe all drugs and devices used in the research, when they will be administered or used, and their purpose.*

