14.0 Number of Subjects

14.1 *Indicate the total number of subjects to be enrolled and how this number was determined (e.g., sample size calculation [show], number of available subjects in a finite pool, number of tests funding award would allow):*

In the preliminary data, we observed effect sizes ranging from $\eta^2 = .027$ to $\eta^2 = .074$. Thus, we selected a medium effect size ($f = 0.25$) to inform sample size of the current study. A total of 112 participants will complete the study (56 participants per group), assuming a type 1 error rate of 0.01 to account for multiple comparisons, 95% statistical power, and pre- and post-measure correlation of 0.25, based on an ANOVA comparing the intervention at sessions 1 and 2.

We anticipate a 70% retention rate; thus, to achieve a final sample size of 112, we anticipate consenting 160 participants.

14.2 If this is a multi-site study, indicate the number of subjects to be enrolled at this site and the total to be enrolled from all sites:

NA

14.3 If applicable, indicate the number of potential subjects you expect to screen for enrollment, and the number of subjects you will need to complete the research procedures:

We cannot accurately estimate the total number of potential participants we expect to screen. However, as described above, we anticipate enrolling 160 participants in order to complete a total of 112 participants. Additionally, the first few participants enrolled in the study may be pilots.

14.4 If the study has more than one procedure, indicate the total number of subjects to undergo each procedure separately:

All participants will undergo all sessions unless they withdraw from the study.

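### The randomisation balances arms on discounting rate and sex, but the named ANOVA contains neither as a factor, so the discounting Group x Time test is conservative and loses precision

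*Combined protocol and SAP*

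**What the plan says.** Section 5.1: "Adults with AUD will be randomly assigned to two groups (active or control), balanced by discounting rate and sex". Sections 1.0 and 8.1 repeat the balancing. Section 8.1 gives the timing: "After the first session, participants will be randomized to one of two groups". Session 1 discounting can therefore serve as the balancing variable, and it is also the pre measurement.

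The hypothesis in 2.2 is "We hypothesize a Group (Scarcity vs. Control) x Time (baseline vs. post) interaction". The analysis in 5.2 reads: "We will compare outcome measures using a repeated measures ANOVA with active vs. control narratives as explanatory variables". No section names sex, a discounting stratum or any other covariate as a model term.

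The error rate and correlation appear only in the sample-size text of 14.1: "assuming a type 1 error rate of 0.01 to account for multiple comparisons, 95% statistical power" and "pre- and post-measure correlation of 0.25". The documents do not say how discounting is categorised for balancing (strata, cut-points, blocks or minimisation). Section 8.3 measures discounting for both money and alcohol, and the documents do not say which of the two is balanced.

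**The concern.** With two sessions, the Group x Time test is a two-sample t test on change scores. Change in discounting is tied to its starting value. Balancing on that value makes the arms more alike than chance would, so the difference in mean change varies less from trial to trial. The ANOVA does not know this: its error term is the one for simple randomisation, so its standard error is too large.

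Two things are at stake. The discounting test does not run at the 0.01 that 14.1 states, and its confidence intervals are too wide. The trial also pays for a balanced randomisation and then discards part of the gain at analysis.

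**Working it through.** **Plan's own figure.** Inputs from 14.1: f = 0.25, alpha 0.01, power 95%, correlation rho = 0.25, two measurements. For the within-between interaction, lambda = f² x N x 2 / (1 - rho). At N = 112, lambda = 0.0625 x 112 x 2 / 0.75 = 18.67 on 1 and 110 degrees of freedom, and power is 0.953. At N = 110 power is 0.949, so 112 is the smallest even N. Then 112 / 0.70 = 160. Both stated numbers reproduce. In units of the score SD, the matching difference in change is 4f, so f = 0.25 is 1 SD.

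**Mechanism.** corr(change, Session 1 score) = -sqrt((1 - rho)/2) = -sqrt(0.375) = -0.61.

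**True size.**
- Variance of change used by the model: 2(1 - rho) = 1.5. With 56 per arm, model SE = sqrt(1.5/28) = 0.231.
- Variance that actually applies: 2(1 - rho) - k x R² x (1 - rho)².
- R² is the share of Session 1 variance captured by the balancing: 0.637 (2/pi) for a median split, 0.861 for quartiles, 1 for exact balance.
- k is the share of randomised participants who remain. It is 1 if all loss precedes randomisation and 0.7 if all of the planned 30% follows it.
- R² and the placing of the loss are assumptions; the documents give neither.

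Example, median split, k = 0.7: 1.5 - 0.7 x 0.637 x 0.5625 = 1.249, so true SE = sqrt(1.249/28) = 0.211. The ratio is 0.231/0.211 = 1.096. The critical value 2.62 then acts as 2.62 x 1.096 = 2.87, and the two-sided size is 0.49%.

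| Correlation | Balancing | Size, no loss after randomisation | Size, 30% loss after | SE ratio, 30% loss |
|---|---|---|---|---|
| 0.25 | median split | 0.33% | 0.49% | 1.096 |
| 0.25 | quartiles | 0.19% | 0.36% | 1.137 |
| 0.25 | exact | 0.12% | 0.28% | 1.164 |
| 0.5 | median split | 0.51% | 0.64% | 1.061 |
| 0.5 | quartiles | 0.38% | 0.53% | 1.085 |
| 0.7 | median split | 0.68% | 0.77% | 1.035 |
| 0.7 | quartiles | 0.59% | 0.70% | 1.049 |

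**Simulation.** At 0.25 with 30% loss, separate simulations gave sizes of 0.38 to 0.55% for a median split and 0.34 to 0.46% for quartiles. Standard errors were about 8 to 15% too large, and nominal 95% intervals covered about 97 to 98%. Without balancing, the simulated size was 1.0%. With the balancing factor in the model it returned to about 1%.

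**If another score is balanced.** Suppose the balancing score correlates 0.6 with the analysed one (assumption; for example, the other commodity). With a median split and 30% loss, the removed variance is 0.7 x 0.637 x 0.36 x 0.5625 = 0.090. The SE ratio is sqrt(1.5/1.410) = 1.03, and the simulated size is 0.81%.

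**Power.** Unadjusted power is about Phi((delta - 2.62 x 0.231)/true SE).
- At the planned 1 SD, median split with loss: Phi(0.393/0.211) = 0.97. Simulation without loss gave 0.970.
- At eta-squared .027, f = sqrt(.027/.973) = 0.167 and delta = 0.67 SD. Simulated power is about 61% unadjusted and 74 to 79% with the strata in the model (median split to quartiles).

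**The case against.** The strongest reply is that the error is on the safe side and its size is conditional. False positives stay below 1%, the stated N reproduces, and power at the planned effect exceeds 95%. The low power at eta-squared .027 comes mainly from the effect size: with neither balancing nor adjustment it would be about 60% (lambda = 0.02775 x 112 x 2 / 0.75 = 8.29), and the plan chose to power for f = 0.25. All of that stands.

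It also stands that Session 1 discounting is not absent from the analysis. It enters as the pre score, and the change score fixes its slope at 1. A reader might infer that the plan ignores both factors altogether. For discounting as an outcome that is too strong; what is missing is the balancing factor as a model term.

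A reader might also infer one figure for the true size, such as 0.3 to 0.4%, as a property of the plan. The documents do not support this. The figure needs a balancing scheme, a placing of the loss, identity of the balanced and analysed scores, and a correlation of 0.25. The first three are unstated, and the fourth is a planning assumption.

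The reply does not remove the mismatch. In every scenario where the analysed score is balanced, the test runs below its stated level and its intervals are too wide.

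**Conclusion.** The concern holds as a conservative error in the discounting analysis. If the balanced score is the one analysed, the nominal 1% test runs at about 0.1 to 0.55% at a correlation of 0.25. At 0.5 to 0.7 it runs at about 0.4 to 0.9%, allowing for simulation spread around the tabulated values. It is nearer 1% if another discounting score is balanced. Standard errors are roughly 8 to 15% too large at 0.25 with the planned loss; the exact-balance limit of the formula is 16%. These figures assume normal scores, random loss and no sex effect on change.

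A reader might infer inflated false positives, an underpowered trial, or damage to all four primary endpoints in 4.1. The documents support none of these. Type 1 error is below nominal, and planned power is met. For demand, craving and time perception, and for sex, the size depends on correlations with change that the documents do not give. The demonstrated cost is lost precision on discounting, and lost power if the true effect is near the low end of the preliminary range in 14.1.

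**What to change.** In 5.2, add the balancing factors exactly as used in the randomisation (discounting rate and sex), each with its interaction with Time, to the primary endpoint models. A main effect alone leaves the Group x Time test unchanged. The equivalent form is to enter them as covariates in a model for the change score. For discounting itself, if the Session 1 value of the analysed score is the covariate, a model for the post score gives the same group test.

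In 5.1 or 8.1, state the balancing method (strata and cut-points, blocks, or minimisation) and whether money or alcohol discounting is balanced.

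The cost is a few sentences and a few degrees of freedom out of 110: two for a median split plus sex, four for quartiles plus sex. No new data are needed.

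### The planned Group x Time ANOVA leaves Session 1 out as a covariate; at the plan's own correlation of 0.25 its model variance is 1.6 times that of an ANCOVA

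*Combined protocol and SAP*

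**What the plan says.** Section 5.2 of the combined protocol and SAP states: "We will compare outcome measures using a repeated measures ANOVA with active vs. control narratives as explanatory variables". Narrative group is the only explanatory variable mentioned, and no section names a baseline covariate.

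Other sections show which effect is tested:

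- Section 2.2: "We hypothesize a Group (Scarcity vs. Control) x Time (baseline vs. post) interaction". The active group is expected to shift, "whereas the control group would not show any changes between baseline and post intervention measures".
- Section 4.1 defines the endpoints as change, for example: "Change in discounting rates will be compared within-subjects across sessions and between groups".
- Section 14.1 sizes the trial with a "pre- and post-measure correlation of 0.25, based on an ANOVA comparing the intervention at sessions 1 and 2", at f = 0.25, type 1 error 0.01 and 95% power. It gives 112 completers, 56 per group.

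On the design, section 5.1 says: "Adults with AUD will be randomly assigned to two groups (active or control), balanced by discounting rate and sex". Section 8.1 places randomisation after Session 1, so the Session 1 value of every outcome is a pre-randomisation measurement. Section 5.2 does not carry the balancing factors into the model.

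**The concern.** With two groups and two time points, the Group x Time F test is the same as a two-sample t-test on change scores. A change score subtracts the whole Session 1 value, whereas an ANCOVA subtracts only the part that predicts Session 2. When the pre-post correlation is low, subtracting the whole value adds noise. At the plan's 0.25, change is noisier than ignoring Session 1 altogether.

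The cost is precision: wider intervals for the narrative effect, and less power if the true effect is smaller than f = 0.25. The plan's own preliminary range includes such effects, and section 3.2 describes the evidence on demand as scarcer than that on discounting.

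There is also a mismatch between design and analysis. Randomisation is balanced on discounting rate and sex, but the standard error from 5.2 ignores the precision this creates. No bias or inflated false-positive rate is claimed.

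**Working it through.** **Inputs.** From 14.1: f = 0.25, two-sided alpha 0.01 (F test), power 95%, correlation rho = 0.25, N = 112 (56 per group), preliminary eta² of .027 to .074. From 2.2: two groups, m = 2 times. Assumption: equal variances at the two sessions, relaxed in step 3. Differences are in SD units of the outcome.

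**1. Reproducing the plan's figure.** For Group x Time, lambda = f²·N·m/(1 − rho) = 0.0625 × 112 × 2 / 0.75 = 18.67 on 1 and 110 df. Power is 95.3%; N = 110 gives 94.9%. So 112 is the smallest equal-arm size for this test. The between-group main effect would need 182, so 14.1 was sized on change across sessions. This f equals a between-group difference in change, delta, of 1.0 SD: lambda = delta² × 28 / 1.5 = 18.67.

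**2. Model variances** (per arm, in units of the outcome variance).

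- Change score: 2(1 − rho) = 1.50
- Session 2 value alone: 1.00
- ANCOVA: 1 − rho² = 0.9375
- Ratio, change to ANCOVA: 1.50 / 0.9375 = 1.60, so the ANCOVA standard error is 1 − 1/√1.6 = 21% smaller

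The ratio simplifies to 2/(1 + rho). Simulation of 8,000 trials per randomisation scheme gave model-variance ratios of 1.58 to 1.60.

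**3. Sensitivity.** Let k be the Session 2 SD divided by the Session 1 SD. The ratio is (1 + k² − 2·rho·k) / (k²(1 − rho²)). It is never below 1, because numerator minus denominator is (1 − rho·k)². The range of k is an assumption.

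| rho | k = 0.8 | k = 1 | k = 1.25 |
|---|---|---|---|
| 0.25 | 2.07 | 1.60 | 1.32 |
| 0.5 | 1.75 | 1.33 | 1.12 |
| 0.7 | 1.59 | 1.18 | 1.02 |

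**4. Interval width at rho 0.25.** The 99% half-width is 2.6213 × √(1.5 × 4/112) = 0.607 SD as planned, and 2.6221 × √(0.9375 × 4/112) = 0.480 SD with ANCOVA.

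**5. Power at N = 112, alpha 0.01, rho 0.25.** For ANCOVA, lambda = delta² × 28 / 0.9375 on 108 df. On the plan's scale f = √(eta²/(1 − eta²)), and delta = 4f.

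| Effect | Planned | ANCOVA |
|---|---|---|
| f = 0.25 (delta 1.0) | 95.3% | 99.7% |
| eta² = .027 on the plan's f scale (f = 0.167, delta 0.666) | 60% | 84% |
| eta² = .074 on the plan's f scale (f = 0.283, delta 1.131) | 98.7% | 99.98% |
| eta² = .027 if partial for the interaction | 20% | 34% |
| eta² = .074 if partial for the interaction | 63% | 87% |

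The plan does not say which eta² it means. In the partial rows the planned lambda is f² × 110 (3.05 and 8.79), and the ANCOVA lambda is that divided by 0.625. That division assumes a correlation of 0.25 in the preliminary data. With 0.5 the ANCOVA figures are 28% and 79%; with 0.7 they are 24% and 72%.

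For a fixed difference of 0.666 SD, the gap narrows as rho rises: 82% against 92% at 0.5, and 97% against 99% at 0.7. For a 1.0 SD difference, ANCOVA reaches 95% power with 72 completers (95.5%; 70 gives 94.9%).

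**6. Delay discounting.** Balancing on the Session 1 discounting rate reduces the true variance of the change-score estimate, but the ANOVA standard error does not reflect it. The documents do not give the balancing method, so these are scenarios: null simulations, 12,000 trials per cell, normal data, equal variances, half of each sex, rho 0.25. Balancing was applied either to 112 people or to the 160 in "We anticipate a 70% retention rate; thus, to achieve a final sample size of 112, we anticipate consenting 160 participants", with 112 kept.

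| Randomisation | Planned type I error (nominal 0.01) | Planned SE too large by |
|---|---|---|
| Simple | 0.0094 | 0% |
| Median-split discounting x sex, blocks of 4: 112 of 112 / 112 of 160 | 0.0038 / 0.0047 | 15% / 9% |
| Discounting-ranked pairs within sex: 112 of 112 / 112 of 160 | 0.0014 / 0.0023 | 26% / 17% |

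A separate 20,000-trial run put type I error at 0.0014 to 0.0056. ANCOVA stayed at 0.008 to 0.010. The ratio of true variances, ANCOVA to change, was 0.76 to 0.99 under balancing. If the balanced rate correlates only 0.5 with the analysed one (assumption), the planned standard error is 2% to 5% too large.

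**7. Demand, craving and time perception.** These were simulated at 0.666 SD with block balancing on discounting. Power was 60.3% as planned, 83.8% with ANCOVA on the outcome's own Session 1 value, and 83.6% after adding an unrelated discounting rate and sex. The gain comes from the outcome's own baseline; the balancing factors cost nothing material.

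**The case against.** Nothing here is broken. Hypothesis, endpoints, design and sample size agree with one another, and the planned test reaches its 95% target. At the effect the plan chose, ANCOVA adds 4.4 percentage points of power. All of this stands, and it limits the point to an improvement in efficiency.

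The 1.6 depends on rho = 0.25, one figure given without a source for every outcome. If the true correlation is higher, the gain is smaller and the planned test is itself stronger: at a 1.0 SD difference and rho 0.5, power is 99.6% against 99.97%. That also stands. A lower correlation works the other way: at rho 0.1 the figures are 90% and 99.6%.

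For delay discounting, 1.6 overstates the true precision loss, because balancing already recovers some or nearly all of it. What remains is mainly an overstated standard error, and its size rests on assumed balancing methods. Section 8.3 lists both money and alcohol discounting; if only one rate is balanced, the stronger conservatism applies to that measure alone.

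The ANCOVA powers under the partial reading of eta² are conditional on a correlation the documents do not give, so they should be read as a range.

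None of this favours the unadjusted model. Its model variance is never below that of the ANCOVA, and the covariate is collected before randomisation in any case.

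**Conclusion.** The concern holds, as a change that should be made rather than an error that invalidates the analysis. The planned test is valid and correctly sized on the plan's own inputs, but it uses a pre-randomisation measurement inefficiently.

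The loss is a model variance 1.6 times that of ANCOVA, on the assumptions of rho = 0.25 and equal variances. It falls to 1.18 at rho 0.7, and to 1.02 there if the Session 2 SD is also 1.25 times the Session 1 SD. The practical difference is small at f = 0.25 and considerable at the low end of the preliminary range. For delay discounting the main effect is a conservative test, to a degree that depends on how balancing is done. For the other outcomes the gain comes from their own Session 1 values.

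**What to change.** In 5.2, replace the model sentence with text such as:

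> For each outcome, the primary between-group analysis is an ANCOVA of the Session 2 value on narrative group, adjusted for the Session 1 value of that outcome, for the baseline discounting rate used in balancing (entered once where it is the same variable) and for sex. The adjusted group difference, with its confidence interval, is the test of the narrative effect and answers the Group x Time question in 2.2. Within-group changes from Session 1 to Session 2 are reported as supporting analyses.

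Name the discounting rate that enters as the balancing covariate (money or alcohol), consistently with 5.1. Keep the within-subject comparisons in 2.2, 4.1 and 8.1, and add a clause in 4.1 and in 8.1 saying that they support the between-group test. In 14.1, note that 112 was derived for the change-score test and is conservative for the ANCOVA; the number need not change.

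The cost is a few lines of text and the IRB approval that 9.1 and 19.1 require for any amendment. Residual degrees of freedom fall from 110 to 108 where the balanced rate is the outcome's own Session 1 value, and to 107 otherwise. The critical t moves from 2.6213 to 2.6221 or 2.6226, which costs under 0.05 percentage points of power. No new data, participants or procedures are needed.
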